6.4 INTERIM ANALYSIS AND DATA MONITORING

No formal interim analyses are planned to compare treatment arms (cycle groups) with respect to efficacy or safety prior to formal completion of the trial.

6.5 MULTICENTER STUDIES

This study is conducted at a single center.

6.6 MULTIPLE COMPARISONS/MULTIPLICITY

No multiple comparison adjustments are planned for the safety and tolerability analyses, which are qualitative in nature. No multiple comparison adjustments will be employed for the PK or PD analyses, as the analyses of these endpoints focus more on estimation rather than inferential testing.

6.7 USE OF AN EFFICACY SUBSET OF PATIENTS

Not applicable.

6.8 ACTIVE-CONTROL STUDIES INTENDED TO SHOW EQUIVALENCE

Not applicable.

6.9 EXAMINATION OF SUBGROUPS

Subgroup analyses of daytime ABPM assessments and adverse events will be performed by race (blacks versus non-blacks).

7. ANALYSIS METHODS

7.1 ANALYSIS POPULATIONS

The following analysis populations will be defined for the study:

Safety Population: The Safety Population will consist of all patients who received at least 1 dose of study drug and will be grouped according to actual study drug taken. All safety and tolerability assessments will be performed using the Safety Population.

PK Population: The PK Population will consist of all patients who received at least 1 dose of study drug and had at least 1 postdose PK parameter assessment. All analyses of PK data will be performed using the PK Population.

PD Population: The PD Population will consist of all patients who received at least 1 dose of study drug and had at least 1 postdose PD assessment. All analyses of PD data will be performed using the PD Population.

7.2 PROTOCOL DEVIATIONS

Protocol deviations will be listed by patient.

7.3 DISPOSITION OF PATIENTS

The number and percentage of patients who were included in each of the 3 analysis populations (Safety, PK, and PD), who completed each cycle, completed the study or discontinued early (along with the reasons for discontinuation) will be presented.

In addition, a data listing of patient disposition, including all patients who terminated early, will be presented.

7.4 DEMOGRAPHIC AND BASELINE CHARACTERISTICS

Patient demographics (age, sex, race, ethnicity, weight, height, and body mass index [BMI, defined as weight in kg divided by height in meters squared]) and other baseline characteristics will be summarized for the Safety Population.

If either the PD or PK Population differs from the Safety Population, the presentation will be repeated for the respective populations.

7.5 MEASUREMENTS OF TREATMENT COMPLIANCE

This is an in-clinic dosing study and, therefore no assessment of compliance is necessary. A data listing containing the study drug dosing information will be provided.

7.6 EXTENT OF EXPOSURE

This is an in-clinic dosing study and therefore no assessment of exposure is necessary, other than the data listing of study drug dosing information.

7.7 PHARMACODYNAMIC (PD) ANALYSIS

7.7.1 PD Parameters

The pharmacodynamic parameters are described below:

Ambulatory BP Monitoring

- Change from time-matched baseline in average daytime systolic BP, MAP, diastolic BP, and pulse. The daytime average for any IW-1973 cycle is defined as the average of the 30-minute average ambulatory assessments from the time of dosing on the ABPM assessment day to the end of the 12-hour ABPM recording for that cycle. Time-matched baseline is defined as the average of ambulatory assessments from the time of dosing on the ABPM assessment day of the Placebo cycle (Study Day 2) to the end of the 12-hour ABPM recording.
- Change from time-matched baseline in average daytime systolic BP, MAP, diastolic BP, and pulse by race (blacks vs. non-blacks)
- Change from time-matched baseline in 4-hour averages of MAP, systolic BP, diastolic BP, and pulse. The 4-hour averages are calculated from the time of dosing on the ABPM assessment day, using the 30-minute average values. Baseline is defined as the corresponding 4-hour average on Day 2 of the placebo cycle.

- Change from time-matched baseline in systolic BP, diastolic BP, MAP, and pulse at 30-minute postdose intervals. See Section 9.7 for details on calculation of assessment time intervals. Baseline is defined as the corresponding 30-minute average on Day 2 of the placebo cycle.

Supine Pulse and BP Measurements

- Change from study baseline in supine systolic BP, diastolic BP, and pulse
- Change from time-matched baseline (placebo cycle) in supine systolic BP, diastolic BP, and pulse
- Change from cycle baseline in supine systolic BP, diastolic BP, and pulse
- Change from trough baseline in trough systolic BP, diastolic BP, and pulse. The trough value for each cycle is defined as the 24 hour postdose assessment after the last dose of that cycle. Trough baseline is the last assessment prior to initiation of IW-1973 administration, that is, the Study Day 4 predose assessment
- Change from pre- to post-nitroglycerine dose assessments of supine systolic BP, diastolic BP, and pulse at the follow-up visit

Orthostatic BP Measurements

- Orthostatic changes in systolic BP, diastolic BP, and pulse. An orthostatic measurement is obtained by subtracting the supine measurement from the standing measurement.

Endothelial Function Assessments

- Change from study baseline in RHI
- Change from time-matched baseline (placebo cycle) in RHI
- Change from cycle baseline in RHI
- Change from pre- to post-nitroglycerine dose assessments of RHI at the follow-up visit

Platelet Function Assessments (PFA-100)

- Change from time-matched baseline (placebo cycle) in time to adhesion/aggregation
- Change from cycle baseline in time to adhesion/aggregation

[REDACTED]

[REDACTED]

7.7.2 PD Analysis

Descriptive statistics will be presented for the observed and change from baseline results for the PD parameters at each scheduled timepoint by cycle group. 95% confidence intervals of the mean difference will be included for summaries of change from baseline results.

For orthostatic BP parameters, descriptive statistics will be presented by cycle group for the change from supine to standing measurements at each scheduled timepoint.

7.7.3 Graphical Presentation of PD Data

Boxplots of change from time-matched baseline in daytime, and 4-hour averages of ambulatory mean arterial pressure, systolic BP, diastolic BP, and pulse will be presented by cycle group.

Mean plots of change from time-matched baseline in 30-minute averages of ABPM assessments over time along with the corresponding 95% confidence intervals will be plotted by cycle group.

Mean plots of change from time-matched baseline in supine cuff blood pressure and pulse assessments over time, along with the corresponding 95% confidence intervals will be presented by cycle group. Individual patient plots of change from time-matched baseline in supine cuff blood pressure and pulse assessments as well as change from trough baseline in trough assessments of supine cuff blood pressure and pulse assessments will be plotted over time.

Individual patient plots of RHI values as well as trough RHI values will be plotted over time as patients escalate from placebo through the IW-1973 doses. Furthermore, boxplots of change from time-matched baseline in RHI values and platelet function assessments will also be presented by cycle group.

7.8 PHARMACOKINETIC (PK) ANALYSIS

7.8.1 PK Parameters

The PK parameters listed in Table 2 will be calculated for each patient, whenever possible, if systemic levels of IW-1973 are detectable. PK parameter calculations will be performed using standard methods in widely available software. Plasma concentrations that are below the LLQ will be treated as described in Section 6.3. Actual sampling times will be used in calculations of the PK parameters.

Table 2. Pharmacokinetic Parameters

| Parameter | Description |
|---------------------|---|
| AUC _{tau} | Area under the plasma concentration-time curve during a dosing interval (tau) |
| C _{max} | Maximum observed plasma concentration, occurring at T _{max} |
| C _{trough} | Trough plasma concentration observed at the end of a dosing interval (collected before the next administration) |
| t _{1/2} | Apparent terminal phase half-life |
| T _{max} | Time of maximum observed plasma concentration |

7.8.2 PK Analysis

Plasma concentration of IW-1973 will be summarized using the PK Population for each assessment timepoint by cycle group. PK parameters will be summarized by cycle group using the PK Population.

7.8.3 Graphical Presentation of PK Data

Geometric mean plasma concentrations will be plotted over time by cycle group on a semi-logarithmic scale. Individual drug plasma concentrations will also be plotted over time. Scatterplots of individual C_{max}, AUC_{tau}, C_{trough}, and T_{max} values will be presented by cycle group for the PK population, with means and medians also presented on these graphs when possible.

7.8.4 PK-PD Analysis

In order to assess potential relationships between the PK assessments and the time course of the PD assessments, scatterplots of change from time-matched baseline in daytime averages of ambulatory assessments and time to adhesion (PFA-100) against C_{max}, C_{trough}, and AUC_{tau} will be included for each cycle group using the PK population.

Furthermore, to assess potential relationships between IW-1973 plasma concentrations and PD assessments, scatterplots of change from time-matched baseline in 30-minute averages of ambulatory blood pressure and pulse assessments and change from time-matched baseline in RHI versus nominal time-matched IW-1973 plasma concentration will be presented by cycle group for the PK population.

7.9 SAFETY ANALYSIS

All safety analyses will be performed using the Safety Population.

7.9.1 Adverse Events

All adverse events (AEs) will be coded using the Medical Dictionary for Regulatory Activities (MedDRA) Version 19.1 and will be classified by MedDRA system organ class (SOC), and preferred term (PT).

Treatment-emergent adverse events (TEAEs) are those AEs that started or worsened in severity after the administration of study drug. If it is not possible to determine when the event started due to incomplete start dates/times, it will be assumed to be treatment emergent.

TEAEs will be assigned to the cycle in which they originated. That is, TEAEs that started on or after the first dose of study drug in a cycle but before dosing in the next cycle will be assigned to the treatment received in that cycle. Adverse events that occurred after the Nitroglycerin administration during the follow-up period will be summarized separately.

The number and percentage of patients who experience at least one TEAE as well as those who experience each specific SOC and PT will be presented by cycle group as well as overall using the Safety Population. Subgroup analyses of TEAEs will also be presented by race (blacks vs. non-blacks). Summaries of study drug related TEAEs will also be presented by cycle group.

Prevalent TEAEs in a cycle are defined as TEAEs that either started in or continued into a cycle, and will be presented by SOC and PT for each cycle group using the Safety Population.

For presentation of AE incidence, AEs will be sorted alphabetically by SOC, and within each SOC, by decreasing incidence of PT in the overall group.

In addition, TEAEs, severe TEAEs, drug-related AEs (those that are determined by the Investigator to be related to study drug), serious AEs, AEs that resulted in study discontinuation, and AEs that resulted in death (if any) will be presented in separate listings.

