8. CHANGES IN THE CONDUCT OF THE STUDY OR PLANNED ANALYSES

The following analyses will be performed in addition to those described in the study protocol.

- Change from cycle baseline (defined as the assessment taken prior to drug administration at the beginning of each cycle) will be presented for cuff BP assessments (supine systolic BP, diastolic BP, and pulse), RHI assessments, and platelet function assessments.
- Change from trough baseline (defined as the last assessment prior to initiation of IW-1973 administration, that is, the Study Day 4 predose assessment) will be presented for trough supine systolic BP, diastolic BP, and pulse.
- Subgroup analyses by race (blacks vs. non-blacks) will be performed for daytime ABPM assessments and adverse events.
- Prevalent TEAEs in a cycle, defined as TEAEs that either started in or continued into a cycle, will be presented by SOC and PT for each cycle group using the Safety Population.
- Change from time-matched baseline (placebo cycle) will be presented for blood glucose, serum insulin and QTc-F for each scheduled postdose assessment.
- Change from study baseline in ECG assessments will be summarized only for the predose assessments in each cycle.

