9.2 CONVENTIONS FOR SUMMARIZING ADVERSE EVENTS

The following conventions will be followed in summarizing TEAEs within a cycle group:

- For patient incidence summaries by cycle group, each patient will be counted only once within each SOC, PT, or the overall AE summary within each cycle
- If a patient reported more than one AE within an SOC or PT within a particular cycle, then the TEAE with the highest severity or strongest study drug relationship within each SOC and each PT will be included in the summaries by severity or relationship, respectively.

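### TEAEs are assigned to cycles by start time alone, so no stated by-cycle table shows the dose at which an adverse event worsened

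*SAP*

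**What the plan says.** SAP 7.9.1 gives a definition with two limbs: "Treatment-emergent adverse events (TEAEs) are those AEs that started or worsened in severity after the administration of study drug". Protocol 3.9.3.4.1 has the same definition. The allocation rule that follows in the SAP has one limb: "TEAEs will be assigned to the cycle in which they originated". The SAP explains it by start time only: "TEAEs that started on or after the first dose of study drug in a cycle but before dosing in the next cycle" take that cycle's treatment label. The date of worsening is not mentioned.

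The same section plans three by-cycle outputs:
- TEAE incidence by SOC and PT, by cycle group and overall.
- Drug-related TEAEs: "Summaries of study drug related TEAEs will also be presented by cycle group".
- A prevalence table: "Prevalent TEAEs in a cycle are defined as TEAEs that either started in or continued into a cycle". SAP 8 lists it among the analyses added to the protocol and says that these events "will be presented by SOC and PT for each cycle group using the Safety Population". Neither section mentions severity or relatedness for this table.

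SAP 9.2 refers to summaries by severity or relationship. When a patient has more than one event in an SOC or PT within one cycle, "the TEAE with the highest severity or strongest study drug relationship within each SOC and each PT will be included". SAP 7.9.1 also plans individual listings, including severe, drug-related and serious events and those leading to discontinuation.

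On data capture, Protocol 3.7.3.5.2 asks the investigator for a severity rating for each event. Protocol 3.7.3.7 starts collection at consent and has a condition present at screening reported as an adverse event if it deteriorates. Neither document says whether an on-study event that worsens is dated at the change or entered again.

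**The concern.** The definition admits worsening, but the allocation rule ignores it. Every patient is planned to take placebo and then 10, 20, 30, 40 and 50 mg in that order, three days each, so an event lasting more than a few days crosses into a new dose level. If it intensifies there, the incidence and drug-related tables leave it at the dose where it first appeared.

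This bears on the first study objective, the safety and tolerability of escalating doses. Protocol 3.5.2 adds the aim of learning whether gradual escalation improves tolerability, and notes that the top planned dose is above the maximum tolerated in healthy volunteers. The dose at which symptoms intensify is part of the answer to that question.

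**Working it through.** The plan has no power, alpha or event-rate figure to reproduce; SAP 4 sets N = 12 outside statistical considerations. The check compares the rules and then tabulates an example.

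**Step 1: rules side by side.** Three kinds of TEAE, each kept on one record:
- *Starts in a cycle and does not worsen.* It has an onset cycle, and the rule works.
- *Starts in one cycle and worsens in a later one.* The rule gives the onset cycle only.
- *Starts between consent and Day 1 and worsens on drug.* It is a TEAE by the second limb, but it started in no cycle and so has no incidence column.

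**Step 2: worked example.** Assumptions for illustration: k of 12 patients have an event that starts at 20 mg, persists, worsens at 40 mg and ends in that cycle; all 12 are in each denominator; these patients have no other TEAE of that term. Each cell is k/12.

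| Tabulation | 20 mg (k = 1, 2, 3) | 30 mg (k = 1, 2, 3) | 40 mg (k = 1, 2, 3) |
|---|---|---|---|
| Onset rule (incidence table) | 8.3%, 16.7%, 25.0% | 0% | 0% |
| Prevalent-TEAE rule | 8.3%, 16.7%, 25.0% | 8.3%, 16.7%, 25.0% | 8.3%, 16.7%, 25.0% |
| Onset, plus worsening counted in its own cycle | 8.3%, 16.7%, 25.0% | 0% | 8.3%, 16.7%, 25.0% |

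Per patient, the shortfall at 40 mg is 1/12 − 0 = 8.3 points in the incidence table and 1/12 − 1/12 = 0 in the prevalent table. The 20 mg column is the same in all three rows.

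**Step 3: what the prevalent table cannot show.** Its row in the example would be identical if the event had stayed mild throughout. Only the third row separates 40 mg from 30 mg.

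**Step 4: chance that it arises.** The documents give no rate. If each patient independently has probability p of such an event, the chance of at least one among 12 is 1 − (1 − p)^12:
- p = 0.05: 0.46
- p = 0.10: 0.72
- p = 0.20: 0.93
- p = 0.30: 0.99

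**The case against.** The strongest reply is the prevalent-TEAE table. A reader might infer from the onset rule that the plan as a whole understates intolerance at higher doses. The documents do not support that: a continuing event is counted at each dose it reaches, and the shortfall there is zero. That table can even err the other way, because it carries a mild, unchanged event from placebo into every later column.

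A reader might also infer a two-column swing of 2/12 = 16.7 points, with the lower dose inflated as well. That does not hold. The event did begin at the lower dose and belongs there, so only the higher-dose column is short, by 1/12.

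A third tempting reading is that an event mild on placebo and severe at 50 mg would be tabulated as a severe placebo event. That requires one record holding only the worst grade, which neither document states. The highest-severity convention in SAP 9.2 does not produce it, because it chooses among several events within the same cycle and does not carry a grade back from a later one. If single-record capture were used, any by-severity summary would show the worst grade under the onset cycle.

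Two further replies carry some weight. If sites enter a worsened event as a new record, the start-based rule already places it correctly, and deterioration of a condition present at screening is already reported as an adverse event. But no such instruction is given for events arising after screening, and the worsening limb of the definition matters mainly when an event stays on its original record. Second, the analysis is descriptive, listings are planned, and table specifications sit in a separate document not available here (SAP 1). This lowers the importance. It does not close the gap, since a listing cannot recover a date of worsening that was never captured.

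**Conclusion.** The point holds as a limited defect in the by-cycle safety tables. The incidence and drug-related tables never credit a worsening to the dose where it occurred, and a worsened pretreatment event has no cycle. The prevalent table counts the continuing event but is not stated to show its severity or relatedness, so no stated by-cycle table identifies the dose at which it worsened.

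The size is up to 8.3 points (1/12) per affected patient in the higher-dose incidence column, and nothing in the onset column or the prevalent table. This assumes that worsening stays on the original record, that all 12 patients are in the denominator, and that the patient has no other TEAE of that term starting in the higher-dose cycle. It should be corrected because it touches the first objective, but it does not invalidate the planned safety analysis.

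**What to change.** In SAP 7.9.1:
1. Keep each TEAE in its cycle of onset. When its severity increases, also count it, at the new severity, in the cycle of worsening.
2. Assign an event that began before Day 1 and worsened on drug to the cycle of worsening.
3. Add maximum severity and relatedness during the cycle to the prevalent-TEAE table, and amend its description in SAP 8 to match.

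In the eCRF completion instructions, require each increase in severity to be dated or entered as a new adverse event row.

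The cost is SAP wording, an eCRF completion note and slightly more tabulation, with no added visits or patients. The downside is that one event may contribute to two cycle columns. Each patient would still be counted once per cycle, as SAP 9.2 requires, and once in the overall column; a table footnote should say so.

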1. INTRODUCTION

Study C1973-201 is a Phase 2a, open-label, single-center study in patients with Type 2 diabetes, hypertension and impaired endothelial function to evaluate the effect of escalating doses of IW-1973 on tolerability, endothelial function, and hemodynamics.

This statistical analysis plan (SAP) provides a more technical and detailed description of the data presentations and statistical analyses of the data as outlined and/or specified in the final protocol for Study C1973-201 (C1973-201-P-03, dated 09 January 2017). Specifications of tables, figures, and data listings are contained in a separate document.

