3. STUDY DESIGN

3.1 GENERAL DESCRIPTION

This open-label, single-center trial will enroll 12 patients (at least 4 men and 4 women) to receive once-daily study drug for 6, sequential, 3-day dosing cycles (18 total days) starting with placebo (baseline) for 3 days and then progressing to 5 escalating dose levels of IW-1973 (10, 20, 30, 40, and 50 mg) for 3 days each. Patients will be in clinic for 20 days, from Check-in on Day -1 to Discharge on Day 19. Total patient participation will be 45 to 77 days.

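### SAP 7.9.1 gives no end to the TEAE window of the last cycle received; applied literally, the 50 mg column covers about 16 days against 3 for every other cycle

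*SAP*

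**What the plan says.** SAP 7.9.1 states the principle, "TEAEs will be assigned to the cycle in which they originated", and then spells it out: the treatment of a given cycle is credited with "TEAEs that started on or after the first dose of study drug in a cycle but before dosing in the next cycle". It names one later boundary: "Adverse events that occurred after the Nitroglycerin administration during the follow-up period will be summarized separately".

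The number and percentage of patients with TEAEs "will be presented by cycle group as well as overall using the Safety Population". The same section adds: "Summaries of study drug related TEAEs will also be presented by cycle group". A further table of prevalent TEAEs counts events that began in a cycle or carried over into it.

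No other text closes the last window:
- The TEAE definition (SAP 7.9.1; Protocol 3.9.3.4.1) has a start but no upper time limit.
- The AE conventions in SAP 9.2 to 9.5, and the list of changes in SAP 8, add none.
- AEs are collected up to the End of Trial Visit (Protocol 3.7.3.7).
- The summary groups in SAP 6.1 are placebo and the five doses, with no follow-up group.

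SAP 7.6 says that "no assessment of exposure is necessary, other than the data listing of study drug dosing information". SAP 1 notes: "Specifications of tables, figures, and data listings are contained in a separate document". Those specifications are not among the documents reviewed.

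**The concern.** A rule that closes each window at dosing in the next cycle cannot close the last one. For a patient who completes the escalation, that is the 50 mg cycle. For a patient who stops early, it is whichever dose came last. If post-discharge events are credited to that dose, its column collects events over a much longer period than the others, and no time-at-risk adjustment is planned to offset this.

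Safety and tolerability of escalating doses is the first objective listed in both documents. Protocol 3.5.2 includes 50 mg, above the maximum tolerated dose in healthy volunteers, because gradual escalation may make it tolerable. That is the column with the open window. A reader comparing percentages from left to right could take an effect of window length for an effect of dose.

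**Working it through.** **Inputs**
- First days of the cycles: 1, 4, 7, 10, 13 and 16 (Protocol 3.8.2.2). Discharge is on Day 19 (Protocol 3.8.2.5).
- Follow-up Visit 14 (±2) days and End of Trial Visit 28 (±3) days after the final dose (Protocol 3.1).
- Nitroglycerin is given at the Follow-up Visit (SAP 3.3).
- 12 patients (SAP 3.1).
- Early stoppers return at the same intervals after their own final dose (Protocol 3.6).

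**The plan's own days.** Final dose: 16 + 2 = Day 18. Follow-up Visit: 18 + 14 = Day 32. End of Trial Visit: 18 + 28 = Day 46. The last two match Protocol 3.1.

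**Window length on the literal reading** (close minus open):

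| Cycle | Opens | Closes | Days |
|---|---|---|---|
| Placebo | 1 | 4 | 3 |
| 10 mg | 4 | 7 | 3 |
| 20 mg | 7 | 10 | 3 |
| 30 mg | 10 | 13 | 3 |
| 40 mg | 13 | 16 | 3 |
| 50 mg | 16 | 32 (30 to 34) | 16 (14 to 18) |

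- Ratio to another cycle: 16/3 = 5.3 (14/3 = 4.7 to 18/3 = 6.0).
- Part of the 50 mg window after discharge: 32 − 19 = 13 days (11 to 15).
- Person-days for 12 completers: 12 × 16 = 192 (168 to 216) at 50 mg, against 12 × 3 = 36 in each other cycle.
- Share of the time from first dose to nitroglycerin: 16/31 = 52% (14/29 = 48% to 18/33 = 55%), against 3/31 = 10% for each other cycle.

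**Early stoppers.** With the final dose on cycle day d, the window is (d − 1) + 14 days: 14, 15 or 16 for d = 1, 2 or 3 (each ±2). These days fall in a lower-dose column, so window length also varies between patients within a column.

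**If nitroglycerin is not given.** The only limit left is the end of AE collection: 46 − 16 = 30 days (27 to 33) for a completer. SAP 3.3 plans nitroglycerin for all patients, so this is an exception, but the rule should cover it.

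**Effect on incidence.** The documents give neither a background AE rate nor the completeness of AE reporting between Day 19 and Day 32. The size of the effect therefore cannot be computed. Only the direction is clear: more days at risk can only add events to that column.

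**Would a plain 72-hour cut do?** Doses on Days 2 to 18 may fall within 15 minutes either side of the Day 1 clock time (Protocol 3.5.3). Suppose the Day 16 dose is 15 minutes early, the Day 18 dose 15 minutes late, and the Day 19 measurement at 24 h + 15 min. That measurement then falls 48 h 30 min + 24 h 15 min = 72 h 45 min after the Day 16 dose. The Discharge physical examination, ECG and safety laboratory tests have no clock time at all (Protocol 3.8.2.5). A strict 72-hour limit could therefore drop Discharge findings from the last dose.

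**The case against.** The strongest reply is that the literal reading is not the only one. SAP 3.1 describes cycles of three dosing days, and Discharge and the Follow-up Period are separate from them. An event on Day 25 would then have originated in no cycle, and the 50 mg window would be 3 days like the rest. This reading is possible. It does not remove the gap, because TEAEs between discharge and nitroglycerin would then have no stated column.

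Other points stand and limit the impact. SAP 6.6 calls the safety and tolerability analyses qualitative, and any inferential statistics are for description only (SAP 6.1). With at most 12 patients, the TEAE and dosing listings let a reader place late events. The table specifications may already contain a follow-up column. Dose is tied to time in this fixed sequence even with equal windows. For completers, the distortion makes 50 mg look less tolerable, not safer. Crediting post-dose events to the last dose is also a defensible choice: PK samples are planned at both later visits, so off dosing need not mean without exposure. If that choice is intended, the SAP should state it and show the unequal windows.

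A reader might infer that the TEAE tables are the only by-cycle tabulation of tolerability. They are not: SAP 7.9.3 tabulates notable vital-sign and orthostatic changes by cycle, and SAP 7.9.4 does so for ECG parameters.

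**Conclusion.** The gap is real and should be closed. Applied as written, with nitroglycerin as the only later cut, the rule gives the 50 mg column about 16 days (14 to 18) against 3 for each other cycle, and an early stopper's last dose 14 to 16 days (each ±2). By-cycle TEAE incidence is then not comparable across doses. The same open end runs through the drug-related and prevalent-TEAE tables, although investigator causality should soften it in the drug-related one. The 16-day figure assumes the literal reading and treats the nitroglycerin sentence as closing the window, which that sentence does not itself say.

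A reader might infer that AE incidence at 50 mg will be inflated about fivefold, in line with the days. The documents do not support that. It would need a constant background rate and equally complete AE reporting at home and in clinic, and neither is given. SAP 9.2 also counts each patient once per cycle, so under those same assumptions the ratio of patients affected would be smaller than the ratio of days. Nor do the documents show that the 16-day window will in fact be used, since the table specifications may say otherwise.

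**What to change.** In SAP 7.9.1, for summary purposes only:
- End the TEAE window of the last cycle received at the later of 72 hours after that cycle's first dose and completion of the Discharge-day assessments. Discharge findings then stay with the last dose, for completers and early stoppers alike.
- Tabulate later TEAEs, up to nitroglycerin or to the End of Trial Visit if none is given, in a separate post-treatment follow-up column. Keep them in the overall column and the listings.
- Apply the same cut to the drug-related and prevalent-TEAE tables.
- If the table specifications already do this, state the rule in the SAP.

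The cost is a sentence or two and one extra table column; no new data are needed and nothing changes in the conduct of the trial. The downside is that late effects of the last dose appear under follow-up instead of under the dose, though they remain visible. For a patient who stops on cycle day 1 or 2, part of the 72 hours may fall after leaving the clinic. The cut makes window lengths about equal and says nothing about washout.
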